### 6.3 Qualitative Analyses

Qualitative analyses be grounded in Interpretive Phenomenological Analysis (IPA) [177]. Data for qualitative analysis will include transcripts from a convenience sample of group therapy sessions and psilocybin drug sessions, therapist process notes, patients' written accounts of their psilocybin experiences, verbal feedback elicited from patients throughout the study, transcripts from focus groups conducted after the study endpoint, and transcripts from 30-60 minute semi-structured interviews conducted with selected patients after the 6-month follow-up. IPA is widely used in studies of psychological interventions to better understand a patient's experience of their treatment, and is typically used to elicit convergent and divergent themes in studies with small sample sizes [177]. Two investigators with experience in qualitative analysis will at first independently code the same transcripts for prominent themes, followed by comparison of their codes until a consensus is reached on an appropriate coding scheme. A code book will be established which will be used to code further sources. Consensus will be re-established on an iterative basis according to the criteria of the coders and the PI.

### 6.4 Schedule of Procedures and Observations

The study-specific assessments are detailed in this section and outlined in [Section 6 Schedule of Study Procedures and Assessments](#). Screening assessments will be performed on enrollment. Any results falling outside of the reference ranges may be repeated at the discretion of the investigator. All on-study visit procedures are allowed a window of  $\pm 7$  days unless otherwise noted. Treatment or visit delays for public holidays or weather conditions do not constitute a protocol violation.

A written, signed, informed consent form (ICF) and a Health Insurance Portability and Accountability Act (HIPAA) authorization must be obtained before any study-specific assessments are initiated. A copy of the signed ICF will be given to the subject and a copy will be filed in the medical record. The original will be kept on file with the study records.

#### 6.4.1 Phone Screening

Potential subjects will be screened over the phone to assure that they understand the time requirements of the study, they identify as a gay man, they are at least 50 years old, they were diagnosed with HIV prior to 1996, they report experiencing moderate-to-severe symptoms of demoralization on the DS-II and that they report complicated grief on the ICG, and that they do not meet any major exclusion criteria (e.g., history of psychosis or bipolar disorder; recent active suicidal ideation). A brief orientation to the study protocol, including psychoeducation on psilocybin, will be provided to patients who are not excluded. The patient will then be scheduled for an in-person screening and enrollment visit.

## 6.4.2 In-person Screening and Enrollment

Screening procedures and assessments to be completed on day of Enrollment (prior laboratory results from UCSF clinics may be considered instead of performing labs at enrollment if the results are less than 6 months old):

- Demographics questionnaire (Age, ethnicity/race, civil status, years of education, income)
- Vital signs; Physical examination; Complete medical and psychiatric history, including current medication list; Performance status (PPSV2); Mental Status Exam; Cognitive Status (Montreal Cognitive Assessment)
- Complete blood count (WBC, Hgb, Hct, Plt)
- Comprehensive metabolic panel (Na, K, Cl, CO2, BUN, Cr, Gluc, Tbili, Ast, Alt, AlkPhos, TProt, Alb)
- TSH, FT4
- Urinalysis
- Urine toxicology (must be completed on day of Enrollment)
- HIV viral load, CD4 count, CD8 count
- RPR or Treponemal Antibody
- Electrocardiogram (ECG)
- Selected screening portions of Structured Clinical Interview for DSM-5 Clinical Trials Version (SCID-5); sections on current Depressive disorders; lifetime Psychotic disorders, Bipolar disorders and Hallucinogen-related disorders), Structured Clinical Interview for DSM-5 Personality Disorders, self-report version (SCID-5-PD; section on Cluster B disorders)
- Columbia Suicide Severity Rating Scale (C-SSRS): Baseline/Screening (last 12 months)
- ART Medication Adherence Scale (AMAS), Centers for Epidemiologic Studies Depression Scale—Revised (CESD-R), Demoralization Scale—II (DS-II), Inventory of Complicated Grief (ICG), McGill Quality of Life Questionnaire-Revised-Short (MQoL-RS), PTSD Checklist-5 (PCL-5), Schedule of Attitudes towards Hastened Death (SAHD), State-Trait Anxiety Inventory (STAI).

Upon completing a successful in-person screening, subjects will also meet individually with one of the study therapists for 30 minutes to develop rapport and to discuss details about the subject's personal life, such as past and current relationships, family dynamics, and concerns about their disease. Finally, the subject will be placed on the waitlist until 6 subjects are available to start a group.

## 6.4.3 Baseline Assessments (Week 1)

### 6.4.3.1 Baseline Subject Assessments

Baseline assessments will be filled out during an individual therapy session wherein the subject will meet one or both of the group therapists in the week prior to the first group therapy session. Separately, the subject's caregiver/important other will be invited to meet with study staff for a brief interview on their relationship with the subject [see Appendix C for interview guides]. The individual session for the study subject is meant to build trust and rapport with the group therapists, to learn more about the subject's life history and struggles with his health, to elicit the subject's preferences and intentions for the treatment sessions, and to orient the subject further to the intervention protocol. If screening/enrollment measures were completed within 1 week of the baseline assessment, those measures will not need to be repeated.

- AMAS, AUDIT, CESD-R, CTC, DS-II, DUDIT, DUFSS-5, ECR-M16, ICG, IOS, IPIP-OE-20, MAIA-R, MQoL- RS, NR-6, PCL-5, PTGI-SF, SAHD, SCS-R, and STAI. A clinical rater will perform a CGI and C-SSRS(Interval) for each subject.

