### Secondary

1. The difference in pre- and post-treatment mean scores of demoralization, complicated grief, depression, PTSD, shame, anxiety, quality of life, functional social support, post-traumatic growth, openness to experience, attachment security, mindfulness, global clinical impressions and ART medication adherence will trend toward significant improvement. These improvements will be sustained at 3-month follow-up.
2. The difference in pre- and post-psilocybin rates of change of group cohesion and group process will trend toward significant improvement.
3. Qualitative analyses of subject behavior and caregiver/important other reports will lead to greater understanding of the interpersonal mechanisms of action of psilocybin-assisted psychotherapy.

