#### 2.1.2 Exploratory Objectives

- To explore the preliminary efficacy of PA-SEGT for improving demoralization, complicated grief, depression, PTSD, shame, anxiety, post-traumatic growth, quality of life, functional social support, openness to experience, attachment security, social connection, nature relatedness and ART medication adherence in LTAS.
- To explore quantitatively and qualitatively the mechanisms (e.g. group cohesion) through which PA-SEGT addresses demoralization and other mental health outcomes in LTAS.

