Demoralization Scale-II (DS-II)—An abbreviated, 16-item and 3-point version of the well-validated original 24-item Demoralization Scale [160], which is the most widely used self-report measure of demoralization in palliative care patients [29]. The DS-II has two subscales: Meaning and Purpose, and Distress and Coping Ability, and shows both good internal and external validity in palliative care patients [27, 161].

Drug Use Disorders Identification Test (DUDIT) – An 11-item screening tool developed as a parallel to the AUDIT to assess drug consumption, drug use behaviors, and drug-related problems.

Duke UNC Functional Social Support Questionnaire-5 (DUFSS-5)—A 5-item, 3-point Likert, self-report measure of perceived functional social support. The abbreviated 5-item scale has been validated in patients with severe medical illness (advanced cancer or AIDS) [162].

Experiences in Close Relationships scale—Modified 16 (ECR-M16)—A 16-item, 7-point Likert self-report measure of attachment security. The abbreviated 16-item version is reliable and has been validated in patients with severe medical illness (metastatic cancer)[163].

Group Questionnaire (GQ)—A validated self-report 30-item 7-point Likert questionnaire of therapeutic relationships in group therapy [130]. GQ has a three-factor model of group cohesion: Positive Bonding, Positive Working, Negative Relationships, all of which manifest in both member-member and member-leader relationships [164]. GQ was empirically-derived from measures in the AGPA CORE-R Battery [136] that assess therapeutic alliance and cohesion—the two factors known to best predict clinical outcomes of group psychotherapy trials [129].

Group Psychotherapy Intervention Rating Scale (GPIRS)—An empirically-derived observer-rated 48-item instrument that assesses group therapist behaviors that help create and maintain group cohesion [165].

HIV and Abuse Related Shame Inventory (HARSI)—A validated 22-item 5-point Likert scale (“Not at All” to “Very Much”) (Neufeld et al 2012, AIDS Behavior, 16:1063-1074).

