### **6.4.4.3 Group Therapy Sessions #5-10 (Weeks 6-8)**

Patients will undergo six group therapy sessions each 90-minutes long. Video footage of a random sampling of sessions will be analyzed with the HIM, SEGT-TG, IGMIPS and the GPIRS. Prior to each session, patients will be screened for adverse events and evaluated with the CSSR-S. Prior to sessions 5, 7 and 9, participants will fill out the CTC. After sessions 6, 8 and 10, participants will fill out the GQ. At the end of session 5, participants will fill out these questionnaires: CESD-R, DS-II, ICG, PCL-5, HARSI. After sessions 7 and 10, participants will fill out the DS-II and ICG.

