### **8.5.1 Exploratory Analyses**

Change in efficacy measures from pre-treatment to post-treatment to 3-month follow-up will be analyzed with descriptive statistics to represent trends in mean levels. Recognizing that the calculations will likely be underpowered, we will also perform ANOVAs of the secondary outcome measures. To assist in gauging the clinical relevance of these data relative to measurement error, and to overcome some of the limitations of the study's small sample size, Reliable Change Indices (RCI) will be calculated [181]. Data from efficacy measures will also be used to estimate effect sizes and intraclass correlation coefficients for use in larger, future studies.

Change in process measures (e.g., the HIM, QPIRS and GQ) over time will be analyzed with ANOVAs to assess the slopes of individual participants and of the whole sample.

Qualitative thematic analyses will be conducted according to the methods outlined in Section 6.3. Iterative inductive analyses will be performed with the aid of NVivo analytical software.

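### The visit lists and the assessment timeline disagree on whether the shame inventory (HARSI) is collected before treatment, so the hypothesised change in shame depends on which schedule staff follow

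*Combined protocol and SAP*

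**What the plan says.** Shame is one of the constructs the trial sets out to track. Secondary hypothesis 1 in Section 1.4 begins "The difference in pre- and post-treatment mean scores of demoralization, complicated grief, depression, PTSD, shame, anxiety" and expects the gains to hold at 3 months. Section 2.1.2 repeats the aim: "To explore the preliminary efficacy of PA-SEGT for improving demoralization, complicated grief, depression, PTSD, shame, anxiety". Section 6.2 names the instrument, "HIV and Abuse Related Shame Inventory (HARSI)—A validated 22-item 5-point Likert scale", and the Abstract lists it among the secondary outcomes. For the analysis, Section 8.5.1 states: "Change in efficacy measures from pre-treatment to post-treatment to 3-month follow-up will be analyzed with descriptive statistics to represent trends in mean levels". It adds effect sizes and Reliable Change Indices.

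The visit text in Section 6.4 does not supply the first of those time points for HARSI. The enrollment questionnaires (6.4.2) end with "PTSD Checklist-5 (PCL-5), Schedule of Attitudes towards Hastened Death (SAHD), State-Trait Anxiety Inventory (STAI", and HARSI is not among them. The baseline list (6.4.3.1) opens "AMAS, AUDIT, CESD-R, CTC, DS-II, DUDIT, DUFSS-5, ECR-M16, ICG, IOS, IPIP-OE-20" and closes "NR-6, PCL-5, PTGI-SF, SAHD, SCS-R, and STAI". It is in alphabetical order, and HARSI is missing from its place between ECR-M16 and ICG. The first collection in the text is in 6.4.4.3: "At the end of session 5, participants will fill out these questionnaires: CESD-R, DS-II, ICG, PCL-5, HARSI". HARSI then appears at Week 8 (6.4.5.1) and at 3 months (6.4.6.2).

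The timeline table at the end of the document, to which the opening line of Section 6 sends the reader as Appendix A, marks HARSI at Enrollment and at Baseline.

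**The concern.** A change score needs a starting value. This is a single-arm trial without randomization (Section 3.6) and without a control group of group therapy alone (Section 1.3), so each man's own pre-treatment score is his only comparator. A baseline questionnaire that is not given before the first group session cannot be collected afterwards.

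The two schedules give different answers on whether the form is handed out, and the document does not say which prevails. Section 6 points to Appendix A for the timeline, while Section 6.4 says that its own text details the assessments. A coordinator could reasonably build the baseline packet from either.

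At stake is one exploratory result: the change in shame and the effect size that Section 8.2.1 wants to pass on to larger trials. Section 2.2.2 offers no safeguard, because it has no definition of change in shame that would alert staff to the need for a baseline.

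**Working it through.** The plan gives no figure to reproduce: Section 8.2.1 states that power calculations for efficacy are not indicated. The check is a comparison of the two schedules, visit by visit.

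**Step 1. HARSI in the visit text and in the timeline.**

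| Visit | Section | HARSI in visit text | HARSI in timeline table |
|---|---|---|---|
| Enrollment | 6.4.2 | no | marked |
| Baseline (Week 1) | 6.4.3.1 | no | marked |
| Group sessions 1–4 (Weeks 2–3) | 6.4.4.1 | no | a mark falls under session 4; column not secure |
| Drug visit and day after (Weeks 4–5) | 6.4.4.2 | no | see step 2 |
| End of session 5 (Weeks 6–8 block) | 6.4.4.3 | yes | see step 2 |
| Endpoint (Week 8) | 6.4.5.1 | yes | see step 2 |
| Focus group (Week 10) | 6.4.6.1 | no | no mark |
| 3 months | 6.4.6.2 | yes | no mark in the table as read |

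Visit text: 0 occasions before psilocybin and 3 after. Timeline: 2 secure occasions before treatment.

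**Step 2. How far the timeline can be trusted.** The table was read from PDF. Split by column, the HARSI row has marks under Enrollment, Baseline, session 4, the day after psilocybin, and session 9. The last two do not match the text, which gives session 5 and Week 8. Other rows also disagree with the text in this region: the Credibility/Expectancy Questionnaire falls under the day before the drug, although 6.4.4.2 places it on the drug day. The later columns are therefore unreliable, and no error is claimed from them, including the absent 3-month mark. The conflict rests on Enrollment and Baseline alone. A session 4 mark, even if confirmed, would be pre-drug but not pre-treatment, because sessions 1–4 belong to the treatment period.

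**Step 3. Is the omission deliberate?** In the timeline the HARSI row has the same pattern of marks as the CESD-R and PCL-5 rows, and 6.4.4.3 gives all three together at session 5. CESD-R and PCL-5 are in both the enrollment and baseline text; HARSI is in neither. That looks like an item dropped from two lists rather than a decision to start measuring shame after the drug.

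**Step 4. Consequence for the analysis in Section 8.5.1.**

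- Mean change = mean(HARSI at Week 8) − mean(HARSI before treatment).
- Effect size of change = mean change ÷ a standard deviation.
- Reliable Change Index for one man = (his Week 8 score − his pre-treatment score) ÷ standard error of the difference.

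Each contains the pre-treatment score. With the visit lists alone that score is missing for 100% of participants and none of the three can be computed. With the timeline it is missing for 0% by design, and all three can.

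**The case against.** The strongest reply is that Section 6 itself directs staff to the timeline, and the timeline collects the score. All pre-treatment contact takes place at one institution (Section 6.1), so one team would have to use the lists and ignore a schedule cited at the head of the same section. On that view this is a missing word in a list, for one of many secondary outcomes, in a trial whose efficacy analyses are descriptive and whose hypothesis is only of a trend.

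Much of this stands. It shows that the design intended a baseline, and it limits the importance of the point. It does not settle which schedule is used, because no order of precedence is stated and 6.4.3.1 reads as a complete list for that visit.

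A reader might infer more than the documents support:

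- That the trial has no baseline for shame. The timeline provides for one, so total loss is only the worst case.
- That the session 5 score would be used as the baseline, hiding early change. Nothing in the plan proposes this.
- That HARSI alone is missing at session 4. In the table as read, CESD-R, DS-II, ICG and PCL-5 also show a mark there, and 6.4.4.1 lists none of them. That is a question about the whole visit, on columns that are not secure.

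**Conclusion.** The inconsistency is real: the visit text gives no HARSI before psilocybin, while the cited timeline gives it at Enrollment and Baseline. Its effect ranges from nothing, if the timeline is followed, to the loss of every pre-treatment shame score, if the visit lists are followed alone. The documents do not show which schedule staff use.

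The conclusion rests on two assumptions: that the Enrollment and Baseline marks in the timeline are read correctly, and that shame is to be analysed as change from pre-treatment, as Sections 1.4 and 8.5.1 indicate. It concerns an exploratory outcome only; the primary safety and feasibility endpoints in Section 2.2.1 do not use HARSI. It should still be corrected, because the loss could not be repaired afterwards and the correction is small.

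**What to change.** 1. Add HARSI to the baseline list in Section 6.4.3.1 and to the enrollment list in Section 6.4.2, so that both agree with the timeline.
2. In Section 2.2.2, define change in shame as HARSI at Baseline, Week 8 and 3 months, with the Baseline score named as the pre-treatment reference. Section 6.4.3.1 lets enrollment measures completed within 1 week stand in for baseline, so say that the enrollment HARSI is the reference in that case.
3. Check the session 4 questionnaires in Section 6.4.4.1 against the original timeline table as a whole, rather than adding HARSI alone.
4. State which schedule governs if the visit text and the timeline differ.
5. When shame is reported, give the number of men with a pre-treatment HARSI.

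The cost is one word in each of two lists, one endpoint definition and one sentence on precedence. The 22-item form is already in the timeline at both visits, so the intended burden on participants does not increase.

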### 6.4.3.2 Baseline Caregiver/Important Other Assessments

- CORF

## 6.4.4 Treatment Period

### 6.4.4.1 Group Therapy Sessions #1-4 (Weeks 2-3)

Patients will undergo four 90-minute group therapy preparatory sessions (2 per week) that will be audio and video recorded. Video footage of a random sampling of sessions will be analyzed with the HIM, SEGT-TG and the GPIRS. Patients will fill out the GQ after the sessions in Week 2 and 4. A clinical rater will administer the C- SSRS(Interval) to each subject at each weekly study visit.

### 6.4.4.2 Individual Drug Sessions (Weeks 4-5)

Patients will undergo individual drug sessions in which they are administered psilocybin 0.30mg/kg (or 0.36mg/kg) po, with a maximum dose not to exceed that calculated for a BMI of 35 at their height. The drug will be administered following the safety guidelines outlined by Johnson et al [24].

The day prior to the session, patients will be screened over the phone for contraindicated medications and reminded about procedures for the medication visit. **Specifically, participants will be reminded that they cannot drive an automobile for the rest of the day after their medication visit, and they will be advised that if they will take the BART, they should not drive their car to the BART station.**

On the day of the medication visit, patients will arrive at the Langley Porter Psychiatric Institute by 08:00 and be oriented to the drug session room, which will contain a couch for the patient to lie on and aesthetically pleasing décor. Before the medication session starts, participants will complete a urine drug screen and the CrEQ. Participants will then hand over their shoes, keys, wallet and phones to the study therapists for safe keeping; these will all be returned to the patient upon completion of the treatment session.

The entire session will be audio and video recorded for subsequent behavioral analysis and rating of therapist adherence to the therapy protocol. The patient will ingest the psilocybin capsules with 4 ounces of water and then be instructed to lie down on the couch wearing

eyeshades and listening to a preselected music soundtrack via headphones. The subject will be instructed to focus their attention internally and to attempt to interact minimally with the two therapists who will be present in the room throughout the drug session, but will be as non-directive as possible in their interactions with the patient. In the event of a psychologically challenging experience such as significant anxiety or confusion, the therapists will provide verbal reassurance. Patients will have been instructed in the preparatory therapy session to notify the study therapists if during the treatment they feel anxiety or fear.

**In the event of a psychiatric emergency**, verbal de-escalation and physical and/or chemical restraint will be used to maintain the safety of the subject and the therapists, according to the clinical judgment of the on-call study physician. All possible efforts will be made to avoid using restraints of any kind. Subjects will not be allowed to leave the premises until the drug effects have worn off.

During the drug session, vital signs (heart rate and blood pressure) will be recorded at 10 minutes prior to drug ingestion, and then 30, 60, 90, 120, 180, 240, 300, and 360 minutes after drug ingestion.

**In the event of a medical emergency**, subjects will be evaluated by the on-call study physician who will be on-site for all drug administrations. At least one ACLS-certified study clinician will be on-site for all drug administrations. While expected to be rare, the most likely serious adverse event to occur would be a hypertensive crisis. If a subject's blood pressure becomes grossly elevated (SBP >180mmHg, DBP >110mmHG) or unsafe (BP elevations with associated symptoms such as chest pain or shortness of breath), blood pressure will be rechecked immediately in both arms and the on-call physician will be notified if s/he is not already in the treatment room. If the subject is clinically suspected of being in **hypertensive emergency** (with signs of end-organ damage), then the subject will be transported to the UCSF Emergency Department for further evaluation and treatment. The Emergency Department's door is less than a 1 minute walk from the Langley Porter Psychiatric Institute. If the patient is determined to be in **hypertensive urgency** (without clinical signs of end-organ damage), then blood pressure will be re-assessed every 5 minutes while the study physician continues to her/his evaluation for signs of clinical instability, and the study physician may attempt to calm the subject with verbal de-escalation or an anxiolytic (e.g. lorazepam) as transient hypertension is most likely to be due to a challenging psychological experience. If after 20 minutes the hypertensive urgency has not improved, the study physician will evaluate the need for transporting the subject to the Emergency Department for further evaluation and treatment. In the case of **acute chest pain**, the on-call study physician will have available sublingual nitroglycerin to administer to the subject and an electrocardiogram machine. A crash cart is located in the building, but the goal will be to transport a decompensating patient to the Emergency Department prior to the crash cart becoming imminently necessary. In the event of a suspected **hypoglycemic episode in a subject with diabetes mellitus**, a finger stick blood glucose will be checked on an as needed basis, and fruit or oral glucose tablets will be available.

As the drug effects begin to wear off at the 5-6 hour mark, the therapists will engage the patient in a therapeutic interview to explore the experience (see Appendix C for interview guide); this discussion will also be videotaped. A clinical rater will administer the C-SSRS(Interval). Only once patients are deemed to be free of the acute effects of the drug, and after at least 7 hours have passed since ingestion of the drug, will the participant be allowed to leave the premise in the company of a caregiver who has been instructed on how best to support the patient over the coming days.

The patient and caregiver will be given a study clinician's pager number in case of any clinical event off-site that needs further assessment. Patients must agree not to drive themselves home, nor to drive later that same day after they arrive home. Patients will be instructed to write a detailed account of their experience during the drug session at some point over the next week.

**In the event that a participant did not arrange a friend/family member to accompany them home**, the participant will be required to stay with the study clinicians longer, will be

encouraged to eat, and then the participant will be escorted to the curb by study staff and seen into a taxi/Lyft/Uber that will be instructed to take them home. The participant will also be instructed to call the study MD when they arrive home. All efforts will be made to avoid this situation. In the weeks prior to the medication session, participants will be regularly reminded to arrange for someone to accompany them home.

The following day patients will return to the study site to meet with a study therapist and engage in a therapeutic discussion of their experience for 90 minutes. Patients will complete the MEQ-30, ChEQ, STAI, SAHD, MQoL, and the C-SSRS(Interval) at this visit. Patients may again meet with study staff in person prior to the next group therapy session if they request this or if study clinicians deem it clinically warranted.

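### The text of section 6.4.4.2 names no C-SSRS between group session 4 and psilocybin ingestion, so on the text the last pre-drug suicidality rating is about 1 to 19 days old at dosing

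*Combined protocol and SAP*

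**What the plan says.** Suicidality is rated with the C-SSRS at enrollment and at baseline, and exclusion 8 in section 3.3.2 applies C-SSRS thresholds at entry. Section 6.4.4.1, headed Weeks 2-3, has a clinical rater give the Interval form "to each subject at each weekly study visit".

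Section 6.4.4.2, headed Weeks 4-5, sets out the steps around dosing in this order:

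- The day before, "patients will be screened over the phone for contraindicated medications and reminded about procedures for the medication visit".
- On the day, "patients will arrive at the Langley Porter Psychiatric Institute by 08:00". "Before the medication session starts, participants will complete a urine drug screen and the CrEQ".
- Heart rate and blood pressure are first "recorded at 10 minutes prior to drug ingestion".
- As the effects wear off at 5-6 hours the therapists interview the man. Then comes the only drug-day C-SSRS in the text: "this discussion will also be videotaped. A clinical rater will administer the C-SSRS(Interval".
- "The following day patients will return to the study site", where the C-SSRS is repeated.

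For sessions 5-10, section 6.4.4.3 says: "Prior to each session, patients will be screened for adverse events and evaluated with the CSSR-S".

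Section 4.1.1 advises that psilocybin should generally not be given to people who are acutely suicidal. Section 2.2.1 assesses suicidality by C-SSRS within the primary safety endpoint, and section 8.5 reports it as an incidence.

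**The concern.** Two things are at stake.

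The first is the dosing decision. The protocol gives acute suicidality as a reason not to dose and uses the C-SSRS to screen for it at entry. On the text, nothing re-applies that instrument near the dose. Mental state can change over the interval: some men may have tapered off antidepressants to take part (footnote to exclusion 4), and section 1.1 reports that in palliative care patients demoralization is more strongly tied to suicidal ideation than depression is. That shows relevance only; it gives no rate.

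The second is the safety data. Ideation that first appears between session 4 and ingestion would first be rated after the drug. Section 8.5 would count it, but whether it began before or after the drug would rest on recall and on the investigator's attribution under section 7.4. Attribution has consequences, because under section 8.3 a single severe, potentially related event halts enrollment until a safety review is complete.

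**Working it through.** The plan states no figure for the age of the last pre-drug rating, so there is nothing to reproduce. The range below is derived from the week labels. The documents give no visit weekdays.

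**Inputs**

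- Sessions 1-4: two per week in Weeks 2-3 (6.4.4.1), so session 4 is the second session of Week 3.
- Dosing: Weeks 4-5 (6.4.4.2).
- Week *w* covers days 7(*w* − 1) + 1 to 7*w*. Week 3 is days 15-21, and Weeks 4-5 are days 22-35.
- Assumption favourable to the plan: the rating at each weekly study visit is given at every group session, so session 4 has one.

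**Age of rating = dosing day − session 4 day**

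1. Any day of the week, with sessions 3 and 4 on separate days: session 4 on days 16-21, dosing on days 22-35. Shortest 22 − 21 = 1 day; longest 35 − 16 = 19 days.
2. Weekdays only: session 4 on Tuesday to Friday of Week 3 (days 16-19), dosing on days 22-26 or 29-33. Shortest 22 − 19 = 3 days; longest 33 − 16 = 17 days.
3. As case 1, but with the day-before call and next-day visit also inside Weeks 4-5: dosing on days 23-34. Shortest 23 − 21 = 2 days; longest 34 − 16 = 18 days.

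With the fix, the age is 0 days (drug-day rating before ingestion) or 1 day (day-before call).

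**What the first post-drug Interval rating covers**

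I take Interval to mean the time since the last rating; the documents do not define it. For weekday visits and a rating about 6 hours after ingestion:

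- 3-day gap: 3 × 24 = 72 hours before the drug; post-drug share 6/(72 + 6) ≈ 8%.
- 17-day gap: 17 × 24 = 408 hours before the drug; post-drug share 6/(408 + 6) ≈ 1%.

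Most of the period covered precedes the drug.

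**Appendix A**

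- Columns from Enrollment to the 3-month follow-up: Enrollment and baseline (2), sessions 1-4 (4), day before, drug day and day after (3), sessions 5-10 (6), two follow-ups (2). Total 17.
- The C-SSRS row as extracted has 6 marks, then 'x(post)', then 10 marks. Total 17.
- Only 1 + 6 + 2 = 9 columns follow the drug day, so one of the 10 later marks is surplus.
- The day-before phone screen and the drug-day urine screen fall in the same extracted column, so the columns in this region are displaced.

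Seventeen marks for 17 columns is what would appear if every visit from Enrollment on, the day before dosing included, carried a C-SSRS. The extracted order does not confirm this, because 'x(post)' comes seventh rather than eighth. The table cannot settle the question either way.

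**The case against.** The strongest reply is that section 6 sends the reader to Appendix A for all assessments, and that table may mark a day-before rating. This stands as a limit: the claim can be made about the text only. A reader might infer from the 'x(post)' label that Appendix A confirms there is no pre-dose rating. The broken columns do not support that.

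Second, a pre-dose check may exist elsewhere. Section 5.2 says a medication-session form monitors suicidality during drug sessions. Section 6.4.4.2 uses similar wording for vital signs that include a reading before ingestion, so the form could have a pre-dose item. Neither the form nor the cited safety guidelines are available here. This also stands. If such a check exists, writing it into section 6.4.4.2 costs a sentence.

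Third, the ratings before sessions 5-10 are paired with adverse-event screening after drug exposure. A reader might infer that the protocol holds dosing to a lower standard than talk therapy. The purposes differ, so the contrast shows only that the instrument is practicable before a visit.

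Fourth, safeguards exist. Severe current depression and recent suicidality are excluded at entry, at least one guide is the man's own group therapist, a physician is on site, the investigator can withdraw him, and the C-SSRS is repeated the next day. They lower the risk. None is described in the text as a structured suicidality rating before ingestion.

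The wording about each weekly study visit might be stretched to Weeks 4-5. It sits under the Weeks 2-3 heading, however, and section 6.4.4.2 places its own drug-day rating after the drug.

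**Conclusion.** The point holds on the text. Section 6.4.4.2 names no C-SSRS between session 4 and ingestion, and the last rating it leaves is about 1 to 19 days old at dosing (about 3 to 17 days for weekday visits). That assumes nominal visit weeks and a rating at session 4. The contraindication in section 4.1.1 then rests on unstructured clinical judgment near the dose, and the first post-drug rating cannot by itself separate onset before the drug from onset after it.

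Two stronger readings should be resisted. A reader might add the 7-day visit window in section 6.4 and infer 19 + 7 = 26 days. A visit on day 35 + 7 = 42 falls in Week 6 (days 36-42), when sessions 5 and 6 require their own C-SSRS, so that figure would need those sessions to slip or be missed as well. A reader might also infer that men would be dosed while suicidal. The documents give no rate of new suicidality in this interval, and none is claimed.

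This is a modest gap in a primary safety measure, worth closing because closing it is cheap.

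**What to change.** In section 6.4.4.2, and in Appendix A if it is not already marked there, add a C-SSRS(Interval) either at the day-before call or on the drug day before ingestion, alongside the urine screen and CrEQ. The on-site study physician reviews it against section 4.1.1 before dosing and keeps the decision. Keep the post-dose rating and state that its interval starts at the pre-dose rating. In section 8.5, report post-drug suicidality relative to the pre-dose rating, in addition to the incidence already planned.

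The cost is a few minutes of participant and rater time per man, with a form and a rater already used on the drug day. The rater must also be available in the morning or for the call. Asking about suicide just before dosing could affect 'set', which section 1.3 treats as important. The day-before option avoids this and leaves a 1-day gap. The text changes are a sentence each in sections 6.4.4.2 and 8.5 and at most one mark in Appendix A.
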